10.0 Clinical Events Committee (CEC)

An independent Clinical Events Committee (CEC) will be established prior to study enrollment. The CEC will be comprised of two members from the original Trifecta™ IDE study Data Monitoring Committee which will provide continuity to the adjudication process. These members are independent from the Sponsor, and the participating investigators in this long term follow up study. The CEC consists of a cardiac surgeon and a cardiologist. The cardiac surgeon will be serving as the chairperson.

A CEC Charter will be developed and agreed upon by the Sponsor and both CEC members prior to the review of data. The Charter will describe the functions of the CEC.

The CEC will meet at a minimum, on a bi-annual basis. However, the CEC may convene more often if deemed necessary by the committee and/or the Sponsor.

11.0 Data Analysis

11.1 Primary Endpoint

Freedom from reoperation due to Structural Valve Deterioration (SVD) at year 10 post-implant.

11.2 Secondary Endpoints

1. Freedom from all-cause mortality;
2. Freedom from valve related mortality;
3. Freedom from SVD.

Additionally, NYHA, specific hemodynamic parameters (e.g. for calculating mean gradient, EOA) and confounding factors, including but not limited to demographic data, anticoagulation/antiplatelet therapy, beta blocker and calcium channel blocker use, and coexisting medical conditions will be collected, to the extent possible, to aid and support the interpretation of the analysis.

11.3 Additional Analysis

Summary information will be provided in graphical and/or tabular format. For continuous variables, summary statistics (N, mean, standard deviation, and percentiles) will be provided. For categorical or ordinal variables, the number of subjects having each attribute and the percentage of total subjects used will be presented.

The following analyses will be performed:

1. Survival (Kaplan-Meier) analyses for all primary and secondary end point events occurring in the post-operative period.
2. Number and linearized rates of subjects experiencing primary and secondary end point late events (>30 days post-implant).
3. A summary of specific hemodynamic (mean gradient, effective orifice area) data
4. NYHA functional classification assessment over time

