4.0 Subject Population

4.1 Inclusion Criteria

1. Patient currently has a Trifecta™ valve that was implanted at one of the U.S. or Canadian investigational sites during the Trifecta™ IDE study.
2. Patient met eligibility criteria prior to enrollment in the Trifecta™ IDE study.
3. Patient agrees to complete all required follow-up visits.
4. Patient provided written informed consent prior to any study related procedure, as approved by the governing Institutional Review Board (IRB) or the Ethics Committee (EC) of the investigational site.

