4.4 Sample Size and Study Duration

The long term follow-up study will enroll subjects who were previously implanted with the Trifecta™ valve in the IDE study and meet section 4.1 criteria and will be followed for ten (10) years from their Trifecta™ implant procedure or until a final event, such as valve explant, death, or change in status (e.g. lost to follow-up or withdrawal from study).

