7.2 Study Termination

Each subject will be followed through 10 years post implant or until time of death, explant, lost to follow up, withdrawal or study termination.

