Data summary and analysis will be performed based on all available data. Statistical analysis software SAS version 9.2 (or newer if available) will be used for the analysis, except when otherwise specified.

Valve Event Analysis

Survival (Kaplan-Meier) Analysis for time-associated mortality, valve-related mortality, SVD, and reoperation due to SVD will be based on the time to the first occurrence of the adverse event for each subject. Kaplan-Meier analysis will be performed to evaluate the freedom from adverse events data over time. Adverse events occurring in the postoperative period will be included in this analysis. The time to event will be determined from the date of implant to the first occurrence of the event (for subjects experiencing the event) or to the last date of contact (for subjects not experiencing the event).

Late Serious Adverse Event (Linearized) Rate will be reported for serious adverse events when appropriate, as defined by the number of late events per 100 late patient-years at risk:

$$\text{Linearized Rate (\%/late patient - year)} = \frac{\text{number of late events}}{\text{total late patient - years}} * 100\%$$

Late events are those that occur 31 or more days post-implant. The late patient-years for each subject are calculated from 31 days following implant to the last date of contact or adverse event as appropriate.

Data Presentation

Summary information will be provided in graphical and/or tabular format. For continuous variables, summary statistics (N, mean, standard deviation, and percentiles) will be provided. For categorical or ordinal variables, the number of subjects having each attribute and the percentage of total subjects used will be presented.

The following data will be presented when necessary:

1. Age at implant
2. Gender
3. Valve size
4. Medical history

The following analyses will be performed:

1. Survival (Kaplan-Meier) analyses for all primary and secondary end point events occurring in the post-operative period.
2. Number and linearized rates of subjects experiencing primary and secondary end point late events (>30 days post-implant).
3. A summary of specific hemodynamic (mean gradient, effective orifice area) data
4. NYHA functional classification assessment over time

Ad hoc analyses may be performed as appropriate.

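### Late-visit NYHA and hemodynamic summaries in effect describe subjects still alive, in the study and with the valve in place, so a comparison across visits can look stable partly through selective loss

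*Combined protocol and SAP*

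**What the plan says.** The analysis lists in section 11.3 and Appendix A (Data Presentation) are the same. Item 3 is "A summary of specific hemodynamic (mean gradient, effective orifice area) data" and item 4 is "NYHA functional classification assessment over time". Continuous variables get N, mean, SD and percentiles. For categorical variables, "the number of subjects having each attribute and the percentage of total subjects used will be presented". The denominator is not defined further. Appendix A adds: "Data summary and analysis will be performed based on all available data".

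Follow-up rules: section 7.2 states "Each subject will be followed through 10 years post implant or until time of death, explant, lost to follow up, withdrawal or study termination". Section 4.4 likewise ends follow-up at ten years "or until a final event, such as valve explant, death, or change in status". Entry under section 4.1 requires that "Patient currently has a Trifecta™ valve that was implanted at one of the U.S. or Canadian investigational sites".

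Prior data: the Appendix A summary keeps IDE and PAS data for eligible subjects at participating sites, including those who died, were explanted or were lost before this study, and those who decline to join it. Section 4.3 is worded more narrowly, for participating subjects, but refers the reader to the SAP.

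Table 7 marks echocardiogram and NYHA at an Early Termination visit. Neither section 11 nor Appendix A says how those values enter the tables. Section 11.2 gives NYHA and hemodynamics a supporting role; they are not listed endpoints.

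**The concern.** A subject who has died or been explanted has no later study-valve gradient and no later NYHA class in this study. If each visit is summarised on the subjects who have a value, the columns describe different groups. Year 3 includes people who will later be explanted or die; year 10 does not.

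A flat mean gradient or a steady NYHA mix can then arise in two ways: little change within subjects, or removal of subjects who were doing worse. The planned tables do not let a reader tell these apart. These summaries are meant to help interpret the SVD and mortality results over ten years, so a stable row beside the SVD curve could be read as stable valve function when part of it reflects who is left.

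**Working it through.** The plan states no figure for this point, so there is nothing to reproduce. The check has two parts.

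**1. Tracing subjects through the plan's rules**

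| Hypothetical subject | Early columns | Late columns |
|---|---|---|
| Dies at year 4 | IDE values and year 3 | none |
| Explanted at year 8 | IDE values and years 3, 5, 7 | no year-10 value; any Early Termination value has no assigned place |
| Does not consent | IDE values (PAS values if in the PAS) | none |
| SVD found by clinical investigation, valve left in place | all | all |
| Alive, valve functioning | all | all |

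The first three rows leave the late columns; the last two stay. So it is explanted valves that drop out, not every deteriorated valve. Appendix B allows SVD to be determined without reoperation, and SVD alone does not end follow-up.

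The Early Termination visit narrows the gap without closing it. Section 7.0 lists echocardiograms only at years 3, 5, 7 and 10 and says only core-laboratory measurements are analysed. Section 7.1 makes years 8 and 9 phone contacts about serious adverse events. A valve explanted between years 7 and 10 may therefore contribute nothing after year 7 unless an Early Termination echocardiogram was done before explant, read by the core laboratory and given a place in the analysis.

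**2. A purely illustrative size for gradient**

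Every input is an assumption: proportion dead by year 10, m; proportion explanted for SVD, e; mean gradient with the valve in place, g0; last gradient before explant, g1; proportion of explants with a usable last value, c. Deaths are left out of both means.

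Mean with last values kept = [(1 − m − e)·g0 + c·e·g1] / [(1 − m − e) + c·e]. With c = 1 the shift from g0 is e/(1 − m) × (g1 − g0). The cohort size cancels.

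With m = 0.30, e = 0.05, g0 = 12 and g1 = 40 mmHg:

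- c = 0: 12.0 mmHg
- c = 0.5: (0.65 × 12 + 0.025 × 40) / 0.675 = 8.8 / 0.675 = 13.0 mmHg
- c = 1: (0.65 × 12 + 0.05 × 40) / 0.70 = 9.8 / 0.70 = 14.0 mmHg

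Range with c = 1, m from 0.30 to 0.50, e from 0.02 to 0.10 and g1 from 30 to 50:

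- smallest shift: 0.02/0.70 × 18 = 0.5, giving 12.5 mmHg
- largest shift: 0.10/0.50 × 38 = 7.6, giving 19.6 mmHg

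If explanted valves failed by regurgitation with a last gradient near 12 mmHg, g1 − g0 is about 0 and so is the shift.

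**NYHA.** No comparable figure is offered. Multiplying the share in class I/II by the share alive with the valve, for example 0.95 × (1 − 0.30 − 0.05) = about 62%, mostly restates assumed mortality and does not measure bias in the NYHA summary.

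**The case against.** The case for leaving the plan alone is reasonable. This is a single-arm descriptive study with no hypothesis on these variables. Durability is judged by CEC-adjudicated SVD and reoperation for SVD, and deaths and failures appear as Kaplan-Meier curves and linearized rates in the same list of analyses. N is shown for continuous variables, so shrinkage is visible. Echocardiogram and NYHA are scheduled at Early Termination.

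Much of this stands, and it rules out several stronger readings that a reader might infer:

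- That the plan restricts the summaries to survivors with the valve in place. No section says so. The late-visit selection is a consequence of the stopping and available-data rules, and the earlier values of subjects who leave stay in the datasets.
- That failed valves as a class disappear. Only explanted ones do.
- That the trend is flattered. It can be. Higher gradients before explant would push that way, but SVD includes regurgitant failure, and many deaths may have nothing to do with valve gradient.
- That a hemodynamic trend is promised. The words about time are attached only to NYHA, although echocardiograms are scheduled at four visits.
- That these tables are the main evidence on valve function. They are supportive.

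What does not answer the point: N shows how many remain, not who left or why, and separate event curves do not alter what the gradient and NYHA columns describe. Keeping prior data of later non-participants makes the early and late groups more different, not less.

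**Conclusion.** The point holds as an inexpensive improvement to supportive tables. The selection follows from the plan's own rules taken together; it is not a stated analysis restriction. Neither direction nor size can be derived from the documents. The 12.5 to 19.6 mmHg range shows only how an answer would depend on explant rate, mortality, last gradient and capture of that value, all of them assumed. The effect of deaths on gradient is uncertain. The primary and secondary Kaplan-Meier endpoints are unaffected.

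**What to change.** In section 11.3 and in Appendix A (Data Presentation):

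- **(a) NYHA.** At each visit use a fixed denominator of implanted subjects due for that visit. Add separate rows for dead, explanted, lost/withdrawn/not consented, and not assessed. Keep the percentage among those assessed next to it, so that mortality is not mistaken for poor functional class.
- **(b) Gradient and EOA.** Also report paired within-subject change from the first post-implant IDE echocardiogram, labelled as conditional on being alive with the valve in place. This removes the change in composition between columns but not the conditioning, since a late value is still needed. The documents do not give the IDE echocardiography schedule, so it assumes that such a baseline is in the datasets.
- **(c) Explanted subjects.** List separately the last core-laboratory gradient and EOA before explant, including the Early Termination echocardiogram where it was done before explant, and state that this is how those values are used.

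No new visits or data collection are needed. The cost is a few sentences in the plan, longer tables and possibly a less favourable picture. Item (c) will be incomplete where no readable echocardiogram precedes explant; the number of such subjects should be shown.

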11.4 Analysis of Scientific Soundness

The scientific soundness of the long term follow up study is established by the following characteristics:

- Principal Investigators and appropriate research staff will be trained on the study protocol and methodologies.
- The purpose of the study is defined.
- Standard definitions are provided for study endpoints.
- Uniform study procedures and echocardiographic methods will be used to ensure consistent measurement of study endpoints.
- The long term follow up study will be conducted in a prospective manner allowing use of current diagnostic methodologies and treatment practices.

- The supporting statistical analysis methods are appropriate for the type of study endpoints and objectives.
- An Echocardiography Core Laboratory will be used.
- The conduct of the study will be monitored on an ongoing basis. Actions to secure and restore compliance will be implemented as appropriate.

12.0 Risk Analysis

12.1 Potential Benefits

Potential benefits to the subjects participating in the study may include study-related assessments including annual transthoracic echocardiograms (TTE) and clinical assessments. Future subjects participating in valve studies may benefit from the experience gained in this long term follow up study.

12.2 Potential Risks

It is expected that the procedures: (TTE, a clinical assessment and the determination of the NYHA functional classification) involve no additional known risks to the subject other than those commonly associated with the follow-up of subjects who have had a prosthetic heart valve implanted.

13.0 Monitoring Procedures

13.1 Study Monitors

All sites will be monitored by Sponsor or Sponsor's designee to ensure the long term follow up study is being conducted in accordance with the protocol, investigator agreement, applicable regulations, and SJM policies and procedures. Only monitors qualified by training and experience who will be trained on the study protocol will be allowed to monitor. The monitor's qualifications and training on the protocol will be documented.

13.2 Monitoring Plan

Prior to initiating site monitoring activities, a study specific Monitoring Plan will be created and revised by the Sponsor as needed over the course of the study.

13.3 Compliance

It is the responsibility of the Sponsor to promptly secure compliance from any site that is not complying with the requirements of this study protocol. If compliance is unable to be secured, SJM may terminate the Investigator's participation in the study.

14.0 Protocol Modifications

14.1 Amendments to the Protocol

If a protocol amendment becomes necessary during the conduct of the study, SJM will submit the amendment to the site and to the respective IRB/EC, as necessary.

14.2 Deviations from the Protocol

Investigators are required to adhere to this protocol, the signed Study Agreement, applicable national or local laws and regulations, and any conditions required by the IRB or REB or appropriate applicable regulatory authorities.

A deviation is used to describe situations in which this protocol was not followed. All deviations must be reported to the Sponsor on the Protocol Deviation Case Report Form. All deviations must be reported to the IRB or EC per their requirements.

15.0 Records & Reports

15.1 Study Sponsor

The Sponsor is responsible for the study design, conduct, analysis, and reporting of the results from this study. The Sponsor is also accountable for monitoring and performing those actions necessary to protect the rights of subjects and the scientific credibility of the manner in which this long term follow up study is conducted. SJM reserves the right to obtain data clarification and/or additional medical documentation on subjects enrolled in this study at any time.

15.2 Study Investigators

The study Investigator is responsible for ensuring that the long term follow up study is conducted according to the Study Agreement and all amendments thereto, Protocol, any conditions of approval imposed by applicable regulatory authorities and/or the reviewing IRB/REBs and all applicable laws and regulations.

15.2.1 Record Retention

Subject study records, correspondence files, all supporting study documentation, and reports as described above must remain on file at the site for a minimum of two years after the termination of this study or per local laws. All Study Investigators must contact SJM prior to destroying or

archiving off-site any records and reports pertaining to this study to ensure that they no longer need to be retained on-site.

16.0 Regulatory Compliance

The Principal Investigator and all research staff participating in this investigation are expected to adhere to the study agreement, the study protocol, the Declaration of Helsinki, 21 CFR parts 50, 54, and 56, applicable Canadian privacy, security and other Canadian laws applicable to the conducting of this study, applicable U.S. Federal and State privacy and security laws.

16.1 Institutional Review Board (IRB)/ Ethics Committee (EC) Approval

A duly constituted IRB/EC representing the prospective study site must review and approve the subject informed consent and research authorization document, the study protocol, the prospective investigator's participation in the study, and any other study related information to be provided to the subjects prior to subject enrollment. Additionally, the Investigator must be aware of and adhere to all IRB/EC requirements such as, but not limited to: the submission of progress reports, serious adverse events, and protocol deviations.

Appendix A: Statistical Analysis Plan

Summary

The long term follow up data of the Trifecta™ valve will be collected for summary and analysis.

In this long term follow up study, subjects who had the Trifecta™ valve implanted as part of the IDE study and enroll (refer to section 4.1) in this study will be followed for a minimum of:

- Ten years post-implant or
- Until time of death, explant, lost to follow-up, withdrawal or study termination.

Additionally, all previously available study data (from Trifecta™ IDE and Trifecta™ post approval study (PAS)) for all subjects (who met eligibility criteria prior to enrollment in the Trifecta™ IDE study) from these participating sites will be included in the analysis datasets for this long term study. This includes prior study data for subjects from these participating study sites who died, were explanted, or were lost to follow-up prior to this long term study as well as prior study data for subjects from these participating study sites who do not consent to participation in this long term study.

The summary data of study primary and secondary endpoints will be provided based on CEC adjudication.

In addition, NYHA functional classification and key specific hemodynamic data will also be provided.

Study endpoints

Primary endpoint

1. Freedom from reoperation due to structural valve deterioration (SVD) at 10 years post implant.

Secondary endpoints

1. Freedom from all cause mortality;
2. Freedom from valve related mortality;
3. Freedom from SVD

Sample size

Approximately 13 sites (among these, 6 sites originally from PAS) who participated in the Trifecta™ valve IDE study with approximately 650 active subjects at the end of the IDE study will be approached for participation in this study.

Analysis Population

Attempts will be made to approach all previous Trifecta™ IDE subjects at the sites participating in the long term follow up study (who were actively being followed and who met eligibility criteria prior to enrollment in the Trifecta™ IDE study) for participation in this study.

In addition to the data collected during this long term follow up study, the study analysis datasets will include all previously available study data (from Trifecta™ IDE and Trifecta™ PAS) for all subjects (who met eligibility criteria prior to enrollment in the Trifecta™ IDE study) from sites participating in the long term follow up study and the PAS.

Data Analysis and Reporting

Data summary and analysis will be performed based on all available data. Statistical analysis software SAS version 9.2 (or newer if available) will be used for the analysis, except when otherwise specified.

Valve Event Analysis

Survival (Kaplan-Meier) Analysis for time-associated mortality, valve-related mortality, SVD, and reoperation due to SVD will be based on the time to the first occurrence of the adverse event for each subject. Kaplan-Meier analysis will be performed to evaluate the freedom from adverse events data over time. Adverse events occurring in the postoperative period will be included in this analysis. The time to event will be determined from the date of implant to the first occurrence of the event (for subjects experiencing the event) or to the last date of contact (for subjects not experiencing the event).

Late Serious Adverse Event (Linearized) Rate will be reported for serious adverse events when appropriate, as defined by the number of late events per 100 late patient-years at risk:

$$\text{Linearized Rate (\%/late patient - year)} = \frac{\text{number of late events}}{\text{total late patient - years}} * 100\%$$

Late events are those that occur 31 or more days post-implant. The late patient-years for each subject are calculated from 31 days following implant to the last date of contact or adverse event as appropriate.

Data Presentation

Summary information will be provided in graphical and/or tabular format. For continuous variables, summary statistics (N, mean, standard deviation, and percentiles) will be provided. For categorical or ordinal variables, the number of subjects having each attribute and the percentage of total subjects used will be presented.

The following data will be presented when necessary:

1. Age at implant
2. Gender
3. Valve size
4. Medical history

The following analyses will be performed:

1. Survival (Kaplan-Meier) analyses for all primary and secondary end point events occurring in the post-operative period.
2. Number and linearized rates of subjects experiencing primary and secondary end point late events (>30 days post-implant).
3. A summary of specific hemodynamic (mean gradient, effective orifice area) data
4. NYHA functional classification assessment over time

Ad hoc analyses may be performed as appropriate.

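### Kaplan-Meier is the only planned time-to-event method for SVD reoperation; a 10-year cumulative incidence beside it would be a cheap improvement

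*Combined protocol and SAP*

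**What the plan says.** The primary endpoint is freedom from reoperation due to SVD at 10 years (sections 3.2.1 and 11.1, Appendix A). The secondary endpoints are freedom from all-cause mortality, from valve-related mortality and from SVD.

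Section 11.3 plans "Survival (Kaplan-Meier) analyses for all primary and secondary end point events occurring in the post-operative period". Appendix A, Valve Event Analysis, repeats that "Kaplan-Meier analysis will be performed to evaluate the freedom from adverse events data over time". Time runs from implant to the first event "or to the last date of contact (for subjects not experiencing the event").

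Three places say what ends follow-up. Section 4.4 follows subjects for ten years or "until a final event, such as valve explant, death, or change in status". Section 7.2 has "until time of death, explant, lost to follow up, withdrawal or study termination", and the Appendix A summary says the same. Appendix B (Reoperation) recognises removal of the valve for reasons unrelated to valve morbidity.

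The Appendix A summary also brings in earlier data on subjects at participating sites who died, were explanted or were lost before this study, and on those who do not consent to it.

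The other planned event summaries are the number of subjects with late endpoint events and linearized rates per late patient-year. Appendix A adds "Ad hoc analyses may be performed as appropriate". Neither the protocol nor the SAP mentions competing risks or cumulative incidence.

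**The concern.** A subject who dies, or whose valve is removed for another reason, can no longer be reoperated on for SVD of that valve. Under the last-contact rule such a subject leaves the risk set like one lost to follow-up. Kaplan-Meier then describes the durability expected if death and other explant did not occur, assuming they are independent of SVD. Its complement, 1-KM, is not the share of implanted patients reoperated for SVD by year 10; it is larger. The plan does not say which quantity is meant and prespecifies no estimate of the second.

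The 10-year freedom figure is the study's headline result, and a reader could take it as a share of patients. The same applies to freedom from SVD and from valve-related mortality, but not to all-cause mortality, which has no competing death.

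A separate matter is the subject who dies of SVD without reoperation. That death is not a failure in the primary endpoint, and cumulative incidence would not change this. If diagnosed, it does count under freedom from SVD and under valve-related mortality.

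**Working it through.** **Is death censored?** No sentence says so. It follows from two rules read together: follow-up stops at death or explant, and subjects without the event contribute time to last contact. No other status is defined for them.

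**Inputs.** The plan has no figure to reproduce: it states no SVD, death or explant rates and no test or performance goal. Its only relevant number is "approximately 650 active subjects at the end of the IDE study will be approached for participation in this study", a count of people to be approached, not the size of the analysis set. Everything else here is assumed:
- F, the 10-year 1-KM for SVD reoperation: 5%.
- S10, the 10-year freedom from all competing events (death and non-SVD explant together): 85%, 70% or 50%, with constant hazard d = -ln(S10)/10.
- SVD hazard h(t): Weibull, shapes 1 (constant) to 4 (late-rising), scaled so that the cumulative hazard H(10) = -ln(1-F). Competing events are independent of SVD.

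**Formulas.**
- Cumulative incidence: CIF(10) = integral from 0 to 10 of h(t) exp(-H(t) - d t) dt.
- Kaplan-Meier 95% half-width: 1.96 (1-F) sqrt[(1/n) x integral from 0 to 10 of h(t) / exp(-H(t) - d t) dt], with n = 650 and censoring by competing events only.

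**Worked case, shape 1, S10 = 70%.** h = -ln(0.95)/10 = 0.00513; d = -ln(0.70)/10 = 0.03567. CIF = [0.00513/(0.00513 + 0.03567)] x (1 - 0.95 x 0.70) = 0.1257 x 0.335 = 4.21%.

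**Results for F = 5%, shapes 1 to 4.**

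| S10 | Cumulative incidence | Gap to 1-KM (points) | Half-width, n = 650 (points) |
|---|---|---|---|
| 85% | 4.62 to 4.39% | 0.4 to 0.6 | 1.7 to 1.8 |
| 70% | 4.21 to 3.77% | 0.8 to 1.2 | 1.8 to 1.9 |
| 50% | 3.62 to 2.90% | 1.4 to 2.1 | 2.0 to 2.2 |

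A simulation of 2 million subjects (shape 3, S10 = 70%) gave 3.84%, the same as the formula. Shape for shape, the gap stays inside the half-width throughout this table. That is not universal: with F = 10% and S10 = 50%, the gap is 2.7-4.2 points against a half-width of 2.8-3.1. Fewer subjects, or further loss, would widen the interval.

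**SVD deaths without reoperation.** Let F now be 1-KM for reoperation or SVD death, and let a constant share p of SVD failures be deaths before reoperation (assumed). Then 1-KM for reoperation alone is 1 - (1-F)^(1-p). With F = 5%:
- p = 10%: 1 - 0.95^0.9 = 4.51%
- p = 20%: 1 - 0.95^0.8 = 4.02%
- p = 30%: 1 - 0.95^0.7 = 3.53%

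Freedom from reoperation would therefore read 95.5-96.5% instead of 95.0%, that is 0.5-1.5 points higher.

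**The case against.** The case for leaving the plan alone is respectable. The stated objective is to collect long-term data on valve-related events, the endpoint is a durability measure, and the documents never promise the proportion of patients reoperated. No hypothesis test depends on the choice. The size of the gap is wholly assumed, and in the illustration it lies inside the sampling error. All of this stands, and it is why the point ranks low. What it does not answer is that the gap is a difference in what is being estimated, which a larger sample would not remove.

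The planned counts also help. With complete follow-up, the number of subjects with a late event over all subjects would be the 10-year cumulative incidence of late events. Loss to follow-up, withdrawal and non-consent make follow-up incomplete, so the counts fill the gap only in part. Linearized rates are averages per patient-year and give no 10-year probability. Ad hoc analyses are allowed, but would not be prespecified.

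A reader might infer something stronger: that Kaplan-Meier is the wrong method here, or that the plan flatters the valve. The documents support neither. Kaplan-Meier is a valid estimate of its own quantity under independence, and 1-KM read as a proportion errs against the valve. Only the SVD-death question runs in the valve's favour. That is a matter of endpoint definition, and diagnosed cases remain visible in the secondary endpoints.

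**Conclusion.** The point holds as a cheap improvement, not an error in the plan, and at the lowest severity. Kaplan-Meier is the only time-to-event method named, competing events are in effect censored, and no 10-year proportion reoperated for SVD is prespecified. For an assumed 1-KM of 5%, the overstatement is about 0.4-0.6 points if 10-year freedom from competing events is 85%, 0.8-1.2 if 70%, and 1.4-2.1 if 50%. These figures assume independent competing events with a constant hazard. The half-width comparison treats 650 as the number analysed. SVD deaths without reoperation are a separate effect in the other direction, whose size rests on an assumed share of 10-30%.

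**What to change.** In section 11.3 and Appendix A:

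- Keep Kaplan-Meier. State that death and non-SVD explant are censored, and label the result as durability with competing events set aside, assuming independence from SVD.
- Prespecify beside it the 10-year Aalen-Johansen cumulative incidence with 95% CI for reoperation due to SVD and for SVD. The competing events are death without the event and explant for other reasons.
- Do the same for valve-related mortality, with other death as the competing event. State how explant is handled, since it ends follow-up while death due to reoperation counts as valve-related in Appendix B.
- Use cumulative incidence for any statement about the proportion of patients.
- Report the number of adjudicated SVD deaths without reoperation beside the primary estimate. Report catheter-treated SVD without reoperation only where the SAE records identify it: Appendix B excludes such therapy from reoperation and asks for the underlying event to be reported, but does not expressly ask for the procedure.

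The cost is a few lines of SAP text and a standard routine. The cumulative incidence needs no new data, because deaths, explants and reasons for reoperation are already collected. The downside is two numbers per endpoint, which need a line of explanation.
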